I agree to ensure that Financial Disclosure Statements will be completed by:

- me (including, if applicable, my spouse [or legal partner] and dependent children)
- my sub investigators (including, if applicable, their spouses [or legal partners] and dependent children)

At the start of the study and for up to one year after the study is completed, if there are changes that affect my financial disclosure status.

I agree to ensure that the confidential information contained in this document will not be used for any purpose other than the evaluation or conduct of the clinical investigation without the prior written consent of Amgen Inc.

Signature

Name of Investigator

Date (DD Month YYYY)

Protocol Synopsis

Title: A Phase 1, Multiple Dose, Randomized, Double-blind, Placebo-controlled Study to Evaluate Pharmacokinetics, Safety and Tolerability of AMG 416 Administered Intravenously to Chinese Subjects with Chronic Kidney Disease on Hemodialysis

Study Phase: Phase I

Indication: Secondary Hyperparathyroidism

Primary Objective:

To characterize the pharmacokinetics of AMG 416 following thrice weekly intravenous (IV) administration of 5 mg in Chinese subjects with chronic kidney disease receiving hemodialysis.

Secondary Objectives:

To characterize the safety and tolerability of AMG 416 following thrice weekly intravenous (IV) administration of 5 mg in Chinese subjects with chronic kidney disease receiving hemodialysis.

Exploratory Objectives:

Hypotheses: This study will adequately characterize the pharmacokinetics profile of AMG 416 in Chinese subjects with chronic kidney disease receiving hemodialysis.

AMG 416 will be safe and well tolerated after multiple dose administration in Chinese subjects with chronic kidney disease on hemodialysis.

Primary Endpoint:

- Pharmacokinetic parameters of AMG 416 in plasma including maximum plasma concentration (C_{max}) and area under the plasma concentration-time curve (AUC_{last}) over the interdialytic interval following the first and last dose.

Secondary Endpoints:

- Incidence of adverse events
- Vital signs, laboratory safety tests including cCa, and ECGs
- Incidence of anti-AMG 416 antibodies

Exploratory Endpoint(s):

Study Design: This is a multiple-dose, double-blind, randomized, placebo-controlled clinical study conducted in Chinese subjects residing in Mainland China with chronic kidney disease receiving hemodialysis. The treatment duration will be approximately 4 weeks with a post treatment follow-up of 4 weeks. A dose will be given at each scheduled hemodialysis session (Dose administered three times a week for 4 weeks, for a total of 12 doses).

Sample Size: Approximately 32 subjects will be randomized in a 3:1 ratio to receive 5 mg IV of AMG 416 or placebo three times a week (TIW) at the end of each regularly scheduled hemodialysis session for 4 weeks (12 doses).

For PK parameter estimation, 2-sided 90% confidence intervals (CI) for geometric means (GM) of PK measurements can be expressed as $(GM/\theta, GM \cdot \theta)$ where θ is a measure of precision. Based on AMG 416 study 20120330 (Cohort 3, 5 mg dose), between-subject CV% for AMG 416 AUC_{last} (hr· μ g/L) and C_{max} (μ g/L) (on original scale) are approximately 50.5% and 52.7%, respectively, following the Day 27 dose. Assuming the same variability for 24 subjects receiving AMG 416 in this study, it is estimated that the precision (θ) of 2-sided 90% CI of geometric mean will be 1.18 and 1.19 for AUC_{last} and C_{max} , respectively.

For safety considerations, with 24 subjects receiving AMG 416, there will be a 21% chance of detecting an adverse event with a true incidence rate of 1% and 98% chance of detecting a more common adverse event with a true incidence rate of 15%.

Summary of Subject Eligibility Criteria:

Male or female subjects ≥ 18 and ≤ 70 years of age at the time of screening, with end stage renal disease receiving hemodialysis with a body mass index between 18 and 35 kg/m² that are residents in Mainland China and of Chinese ancestry, inclusive. Corrected calcium (calculated) level is ≥ 2.07 mmol/L (8.3 mg/dL) and iPTH level is between 31.8 – 127.2 pmol/L (300 - 1200 pg/mL), inclusive at enrollment and subject has not received cinacalcet within the 30 days prior to informed consent.

For a full list of eligibility criteria, please refer to [Section 4](#).

Investigational Product

Amgen Investigational Product Dosage and Administration:

Investigational product will be administered thrice weekly with each hemodialysis treatment for 4 weeks (12 doses). The dose of investigational product is 5 mg. Each subject will receive AMG 416 or placebo administered by bolus injection into the venous line of the dialysis circuit at the end of each of 12 consecutive hemodialysis treatments, prior to or during rinse-back with each hemodialysis session (ie, 3 times per week). At least 150 mL of rinse back volume should be administered after investigational product injection to ensure investigational product reaches the systemic circulation.

For a complete description see [Section 6.3.1](#).

Procedures:

Screening: After providing written informed consent, subjects enter a screening period of 22 days, during which all screening tests required to establish eligibility will be completed. Subjects who meet the eligibility criteria after completion of all screening, Day -2 and Day 1 predose procedures, will be enrolled in the study. Day -2 assessments will be performed 2 days before investigational product administration.

Screening procedures are summarized in the [Schedule of Assessments](#).

Baseline and Treatment: Subjects will return to the research facility for day -2 assessments. Eligible subjects should be randomized to investigational product in a 3:1 ratio to AMG 416 or placebo, and should then receive the first dose. On Day 1, enrolled subjects will receive the first 5 mg IV dose of AMG 416 given after hemodialysis. Following completion of all study procedures on Day 1, subjects will be released with instructions to return to the research facility at specified time points for dosing, collection of blood samples for PK, PD and completion of safety assessments (including blood samples for antibody analysis) through the end of the study according to the [Schedule of Assessments](#).

IP will be administered at the end of dialysis on Study Days 1, 3, 6, 8, 10, 13, 15, 17, 20, 22, 24, 27 (12 doses). Dialysis will continue thrice weekly without study drug administration with study visits for data collection on Study Days 29, 34, 41, 55 (EOS). Blood samples for the determination of PK parameters will be collected on Day 1 and 27 at predialysis, and at 10, 30, 60 and 90 min postdose, as well as on Day 2 and 28 between 18 and 30 h after study drug administration, and at predialysis on Days 3, 8, 15, 22, 29, 34, 41, and 55 (EOS) and at 10 min postdose on Days 8, 15 and 22. Subjects will have blood samples drawn for antibody determination prior to dosing on Day 1 and on days 29 and 55. Blood samples for exploratory

Electrocardiograms (ECG) will be performed at screening, on Day -2, and on days 28 and 55.

The date and time of hemodialysis treatment will be recorded throughout the treatment period. When a visit corresponds to a dialysis day, study procedures should be completed prior to hemodialysis with the exception of dose administration and specified PK sample collection as described in the [Schedule of Assessments](#).

Routine hematology and chemistry safety laboratory tests will be performed periodically. Subjects will be followed for safety throughout the 4-week treatment period and for 4 weeks after the last dose of investigational product. Dosing with investigational product may be suspended, for low predialysis iPTH or cCa, symptomatic hypocalcemia, or other drug-related adverse events.

End of Study

Subjects will be followed through Day 55 (EOS). Subject participation is complete once end-of-study (EOS) procedures are performed. Subjects who test positive for neutralizing antibodies to AMG 416 at the Day 55 EOS visit will be asked to return for additional follow-up testing. This testing should occur approximately every 3 months starting from when the site has been notified of the positive result, until: (1) neutralizing antibodies are no longer detectable or (2) the subject has been followed for a period of at least 1 year (\pm 4 weeks). More frequent testing (eg, every month), or testing for a longer period of time, may be requested in the event of safety-related concerns. Subjects who test positive for binding antibodies and have clinical sequelae that are considered potentially related to an anti-AMG 416 antibody response may also be asked to return for additional follow-up testing.

All adverse events (including serious adverse events and deaths) and use of concomitant medication will be collected for the duration of the study up to and including the Day 55 EOS visit. If there is a clinically significant clinical or laboratory abnormality that requires monitoring, subjects will be followed until resolution of the abnormality, or until it is considered stable.

For a full list of study procedures, including the timing of each procedure, please refer to [Section 7](#) and the Schedule of Assessments ([Table 1](#)).

Statistical Considerations:

Demographics and safety data will be summarized by treatment groups. Unless otherwise stated, the data analysis will be conducted using subjects in the Safety Analysis Set. Descriptive statistics on continuous measurements will include means, medians, standard deviations, and ranges, while categorical data will be summarized using frequency counts and percentages. Pharmacokinetic, vital sign, ECG, and clinical laboratory data will be summarized at each time point when samples are collected.

The number and percent of subjects reporting any treatment-emergent adverse events and each adverse event will be tabulated by system organ class and preferred term and will be further classified by relationship to treatment. Subjects who experience clinically-significant changes in clinical laboratory test values, ECGs, or vital signs will be noted.

Individual and mean (SD) plasma concentration-time plots for AMG 416 will be presented. The PK parameters (eg, interdialytic C_{max} and AUC_{last} on after the first and last dose on Study Days 1 and 27) will be estimated using noncompartmental methods. Nominal dose and actual sampling time data will be used for calculation of PK parameters. Summary statistics will be generated for each PK parameter.

For a full description of statistical analysis methods, please refer to [Section 10](#).

[figure not shown]
Sponsor:

Amgen Inc*
[name]
[contact]

[contact]

*Effective July 5, 2012, KAI Pharmaceuticals, Inc. became a wholly owned subsidiary of Amgen Inc. In connection with Amgen's acquisition of KAI, Amgen Inc. will be managing the clinical study described in this protocol on behalf of KAI.

Study Design and Treatment Schema

^a TIW = Three times a week (12 doses)

^b Last Dose Administration (Day 27)

^c EOS = End of Study will occur on Day 55, PK washout and safety followup (Day 28-55)

Study Glossary

Abbreviation or Term	Definition/Explanation
%CV	coefficient of variation
ADA	Anti-drug antibody assay
ADME	Absorption, distribution, metabolism, and excretion
ALP	alkaline phosphatase
ALT	alanine aminotransferase
API	Active pharmaceutical ingredient
AST	aspartate aminotransferase
AUC	area under the concentration-time curve
AUC _{last}	area under the concentration-time curve from time 0 to the time of the last quantifiable sample
BMI	Body Mass Index
CaSR	Calcium sensing receptor
Ca	Calcium
cCa	Total serum albumin corrected calcium concentration
cCa x P	Corrected calcium-phosphorus product
CHD	Coronary heart disease
CKD	Chronic kidney disease
CKD-MBD	Chronic kidney disease-mineral and bone disorder
CI	Confidence Interval
CK	Creatinine kinase
CL	Clearance
C _{max}	Maximum observed concentration
Corrected Total Serum Calcium (for albumin levels < 4.0 g/dL)	Corrected calcium (mg/dL) = Total calcium (mg/dL) + (4 - albumin [g/dL])*0.8.
CRF	Case report form (electronic or paper)
CTCAE	Common Terminology Criteria for Adverse Events
CV	Coefficient of variation
DILI	Drug-induced liver injury
EDC	Electronic data capture
ECG	Electrocardiogram
End of study for individual subject	defined as the last day that protocol-specified procedures are conducted for an individual subject
End of treatment	defined as the last assessment for the protocol-specified treatment phase of the study for an individual subject

Abbreviation or Term	Definition/Explanation
Enrollment Date	Same as Study Day 1
EOS	End of Study
eSAE	electronic Serious Adverse Event (form)
FDA	Food and Drug Administration
FIH	first-in-human
FSH	follicle-stimulating hormone
GCP	Good Clinical Practice
GGT	gamma-glutamyl transpeptidase
GM	Geometric mean
HBcAb	hepatitis B core antibody
HBsAg	hepatitis B surface antigen
HDL-C	high density lipoprotein cholesterol
hERG	human Ether-à-go-go-Related Gene
HepCAb	hepatitis C virus antibodies
HIV	human immunodeficiency virus
HR	heart rate
ICF	informed consent form
ICH	International Conference on Harmonisation
IFU	instructions for Use
INR	international normalized ratio
Interdialytic AUC _{last}	area under the concentration-time curve measured from the time of drug administration to the beginning of the next dialysis session
Interdialytic C _{max}	maximum drug concentration measured between the time of drug administration to the beginning of the next dialysis session
IP	investigational product
IPIM	investigational product instruction manual
iPTH	Intact parathyroid hormone
IRB	Institutional Review Board
IV	Intravenous
IVR/IWR	Interactive Voice/Web Response System
KDIGO	Kidney Disease Improving Global Outcomes
K/DOQI	Kidney Disease Outcomes Quality Initiative
MCH	mean corpuscular hemoglobin
MCHC	mean corpuscular hemoglobin concentration
MCV	mean corpuscular volume

Abbreviation or Term	Definition/Explanation
MedDRA	Medical dictionary for regulatory activities
mL	Milliliter
mM	Millimolar
n	number of subjects or observations
NKF	National Kidney Foundation
P	Phosphorous
PD	Pharmacodynamic(s)
pg	Picograms
PR interval	PR interval is measured from the beginning of the P wave to the beginning of the QRS complex in the heart's electrical cycle as measured by ECG
PTH	Parathyroid hormone
qhd	Every hemodialysis day
QRS interval	QRS interval the interval between the Q wave and the S wave in the heart's electrical cycle as measured by ECG; represents the time it takes for the depolarization of the ventricles
QT interval	QT interval is a measure of the time between the start of the Q wave and the end of the T wave in the heart's electrical cycle as measured by ECG
QTc interval	QT interval corrected for heart rate using accepted methodology
RI	renal impairment
RR	respiratory rate
SAE	severe adverse event
SHPT	Secondary hyperparathyroidism
Study Day 1	Defined as the first day that protocol specified investigational product(s)/protocol-required therapies is/are administered to the subject
TEMP	Temperature
T _{1/2}	Terminal elimination phase half life
TBL	Total bilirubin
TIW	Thrice weekly
ULN	Upper limit of normal
URR	Urea reduction ratio
Vit D	Vitamin D

TABLE OF CONTENTS

Protocol Synopsis.....	3
Study Design and Treatment Schema	6
Study Glossary	7
1. OBJECTIVES	14
1.1 Primary	14
1.2 Secondary.....	14
1.3 Exploratory.....	14
2. BACKGROUND AND RATIONALE	14
2.1 Disease.....	14
2.2 Amgen Investigational Product Background	15
2.2.1 Nonclinical Experience	15
2.2.1.1 Nonclinical Pharmacology	15
2.2.1.2 Nonclinical Pharmacokinetics, Absorption, Distribution, Metabolism, and Excretion (ADME)	16
2.2.1.3 Nonclinical Toxicology.....	17
2.2.2 Clinical Experience	17
2.2.2.1 Clinical Pharmacokinetics	18
2.3 Risk Assessment.....	19
2.4 Rationale.....	20
2.5 Clinical Hypotheses.....	20
3. EXPERIMENTAL PLAN.....	21
3.1 Study Design.....	21
3.2 Number of Sites	21
3.3 Number of Subjects.....	21
3.4 Replacement of Subjects	21
3.5 Estimated Study Duration.....	22
3.5.1 Study Duration for Subjects	22
3.5.2 End of Study.....	22
4. SUBJECT ELIGIBILITY	22

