3.5 Estimated Study Duration

3.5.1 Study Duration for Subjects

The estimated duration of study participation for each subject is approximately 77 days. This includes a 22-day screening period preceding a 55-day treatment and follow-up period. Subject participation may be adjusted based on treatment-emergent data. All adjustments or modifications to the schedule will be agreed upon by the investigator in consultation with Amgen. The institutional review board (IRB) will be informed via written correspondence and the informed consent form (ICF) will be updated accordingly.

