- ^f Subjects will remain supine for at least 5 minutes prior to recording 12-lead electrocardiogram (ECG). Screening 12-lead ECG will be recorded prior to hemodialysis. The Day -2 12-lead ECG will be recorded within 4 hours after hemodialysis rinse back. After the last dose of investigational product on Day 27, 12-lead ECGs will be recorded between 18 and 30 hours (recorded on day 28) post-dose.
- ^g Adverse events will be monitored and recorded from the dose of investigational product (AMG 416) or placebo. Serious adverse events will be monitored and recorded from the time of informed consent through Day 55.
- ^h After Day 28, hemodialysis will continue on study days 29, 31, 34, 36, 38, 41, 43, 45, 48, 50, 52 and 55; data collection and study procedures will only occur on hemodialysis days 29, 34, 41, and 55(EOS).
- ⁱ Demographic information collected at screening includes sex, age, race, and ethnicity.

Table 1b. Schedule of Laboratory Assessments

Time	Assessment	Study Visit (Day)																			
		Screening	-2	1 (HD)	2	3 (HD)	6 (HD)	8 (HD)	10 (HD)	13 (HD)	15 (HD)	17 (HD)	20 (HD)	22 (HD)	24 (HD)	27 (HD)	28	29/ ET ^a (HD)	34 (HD)	41 (HD)	55 (HD)
Laboratory Assessments																					
Pre HD	Hematology, PT, aPTT ^c	X		X							X							X			X
	Clinical Chemistry	X		X							X							X			X
	Albumin ^d	X	X ^b	X		X		X			X		X		X			X	X	X	X
	Phosphorus	X	X ^b			X		X			X		X		X				X	X	X
	Calcium (cCa) ^d	X	X ^b	X				X			X		X		X			X	X	X	X
	Serum or Urine Pregnancy (females only)	X	X ^b																X		
	Serum FSH ^g (female only)	X																			
	Breath Alcohol Screen	X	X																		
	HIV, Hep C Ab, HBsAg	X																			
	iPTH	X	X ^b	X				X			X		X		X				X	X	X
	25(OH) vitamin D	X																			
	Kt/V or URR ^e	X																			
	Anti-drug antibodies ^f			X														X			X

Footnotes displayed on the next page

HD = hemodialysis; ET = early termination; cCa = albumin-corrected calcium; SDA = Study drug administration ; Kt/V = measure of dialysis adequacy;

URR = urea reduction ratio

- ^a If a treated subject withdraws from study before completion of dosing, the investigator will make every effort to obtain day 29 samples as close to 2 days after the last dose of investigational product as possible.
- ^b If screening albumin, phosphorus, cCa, pregnancy, and iPTH tests occur within 7 days prior to start of IP, then Day -2 lab tests can be waived

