9. SAFETY DATA COLLECTION, RECORDING, AND REPORTING

9.1 Adverse Events

9.1.1 Definition of Adverse Events

An adverse event is defined as any untoward medical occurrence in a clinical trial subject. The event does not necessarily have a causal relationship with study treatment. The investigator is responsible for ensuring that any adverse events observed by the investigator or reported by the subject are recorded in the subject's medical record.

The definition of adverse events includes worsening of a preexisting medical condition. Worsening indicates that the preexisting medical condition (eg, diabetes, migraine headaches, gout) has increased in severity, frequency, and/or duration, and/or has an association with a significantly worse outcome. A preexisting condition that has not worsened during the study, or involves an intervention such as elective cosmetic surgery or a medical procedure while on study, is not considered an adverse event.

The investigator's clinical judgment is used to determine whether a subject is to be removed from treatment due to an adverse event. In the event a subject, or subject's legally acceptable representative requests to withdraw from protocol-required therapies or the study due to an adverse event, refer to [Section 8.1](#) for additional instructions on the procedures recommended for safe withdrawal from protocol-required therapies or the study.

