9.2 Reporting of Adverse Events

9.2.1 Reporting Procedures for Adverse Events That do not Meet Serious Criteria

The investigator is responsible for ensuring that all adverse events observed by the investigator or reported by the subject that occur from the dose of investigational product (AMG 416) through the Day 55 EOS are reported using the applicable CRF (eg, Event CRF).

The investigator must assign the following adverse event attributes:

- adverse event diagnosis or syndrome(s), if known (if not known, signs or symptoms)
- dates of onset and resolution (if resolved)
- severity [and/or toxicity per protocol]
- assessment of relatedness to AMG 416 or other therapies,
- action taken

The adverse event grading scale used will be the CTCAE version 4. The grading scale used in this study is described in [Appendix A](#). The criteria for grade 4 in the CTCAE grading scale differs from the regulatory criteria for serious adverse events. It is left to the investigator's judgment to report these grade 4 abnormalities as serious adverse events.

The investigator must assess whether the adverse event is possibly related to the investigational product. This relationship is indicated by a "yes" or "no" response to the question: "Is there a reasonable possibility that the event may have been caused by the investigational product?"

The investigator must assess whether the adverse event is possibly related to any study mandated activity (eg, protocol-required procedure (including any screening procedure[s])). This relationship is indicated by a "yes" or "no" response to the question: "Is there a reasonable possibility that the event may have been caused by a study activity, and/or procedure?"

The investigator is responsible for reviewing laboratory test results and determining whether an abnormal value in an individual study subject represents a clinically significant change from the subject's baseline values. In general, abnormal laboratory

findings without clinical significance (based on the investigator's judgment) are not to be recorded as adverse events. However, laboratory value changes that require treatment or adjustment in current therapy are considered adverse events. Where applicable, clinical sequelae (not the laboratory abnormality), are to be recorded as the adverse event.

If the severity of an adverse event changes from the date of onset to the date of resolution, record as a single event with the worst severity on the Event CRF.

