#### Treatment Emergent Adverse Events (TEAE)

Adverse events (AEs) starting on or after the first dose of IP as determined by the flag indicating if the adverse event started prior to the first dose of IP on the Adverse Events Summary CRF and up to 30 days after the last dose date or EOS date, whichever is **earlier**.

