### 8.3 Handling of Missing and Incomplete Data

Subjects may be missing specific data points for various reasons. In general, data may be missing due to a subject's early withdrawal from study, a missed visit, or non-evaluability of a data point at a particular point in time. Sites will be queried for missing or non-conformant data that are required or considered critical. All efforts will be made to capture complete critical data prior to the database lock.

The following imputation rules will be implemented for critical data if the missing or incomplete data cannot be resolved after the query process:

Only missing or partially missing dates for adverse events will be imputed with the exception of adverse events occurring prior to the first dose date. Stop dates for AEs will not be imputed. Adverse events with a partially missing start date that is conclusively prior to the date of first IP administered (as indicated by 'Did event start before first dose of IP' on the AE CRF page) will be considered pre-treatment adverse events and excluded from safety analyses. All other partially missing adverse event start dates will be handled as described below, with the reference date being Study Day 1:

- If the year is available and the day and month are missing, the day and month will be set to the 1st of January of the onset year
- If the year and month are available and the day is missing, the day will be set to the 1st of the onset month
- If the day and month are available and the year is missing, the year will be set to the year of the reference date
- If the year and day are available and the month is missing, the month will be set to January of the onset year
- If the resulting date is prior to the reference date, the date will be reset to the reference date (this applies to AE start date imputation only)

Partial/missing start dates for concomitant medications of interest will be imputed using the algorithm above with the reference date being Study Day 1. Partial/missing stop dates for these concomitant medications will be imputed using the following logic:

- If the medication stop date is completely missing, then the stop date is set as the end of the study date
- If the stop year is available and stop month and day are missing, the month and day will be reset to 31st of December of the stop year
- If the stop year and month are available and the stop day is missing, the stop day will be set to the last day of the month of the stop year

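### An adverse event already recorded before first dose that worsens on treatment drops out of the TEAE tables unless the site enters the worsening as a new event

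*Protocol*

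**What the plan says.** **When collection starts.** Under its End of Study heading, the protocol synopsis states: "All adverse events (including serious adverse events and deaths) and use of concomitant medication will be collected for the duration of the study". It gives the end (Day 55) but no start. Section 3.5.1 counts screening as part of participation: "This includes a 22-day screening period preceding a 55-day treatment and follow-up period". The Day 1 predose list in Section 7.2.3 has AE monitoring with no restriction to serious events.

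The operational text is narrower. Table 1a footnote g says: "Adverse events will be monitored and recorded from the dose of investigational product (AMG 416) or placebo". Section 9.2.1 agrees, covering non-serious events "that occur from the dose of investigational product (AMG 416) through the Day 55 EOS are reported using the applicable CRF". The screening and Day -2 lists (7.2.1, 7.2.2) mention SAE monitoring only, and Section 9.2.2 collects SAEs from consent.

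**How a change in severity is recorded.** If severity changes between onset and resolution, Section 9.2.1 tells the site to "record as a single event with the worst severity on the Event CRF". It asks for no date of worsening.

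**What counts as an AE.** Section 9.1.1: "The definition of adverse events includes worsening of a preexisting medical condition". Table 1a footnote c applies the same principle to hemodialysis symptoms captured at screening.

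**What counts as treatment-emergent.** SAP 5.4 takes those events "starting on or after the first dose of IP as determined by the flag indicating if the adverse event started prior to the first dose". It has no clause for an event that was present before dosing and worsens afterwards. SAP 8.3 says that events with a partially missing start date that is conclusively before first dose "will be considered pre-treatment adverse events and excluded from safety analyses". SAP Section 10 declares no change from the protocol's analyses.

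**The concern.** The protocol treats worsening as an adverse event, but the SAP selects events by start date alone. When an event is already on an AE record at first dose, the single-record rule attaches any later deterioration to a record with a pre-dose start. The flag then removes the whole record from the TEAE tables, including the on-treatment grade.

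Two kinds of record are exposed. One is an SAE that begins between consent and first dose. The other is a non-serious AE entered before dosing because the site worked from the synopsis sentence or the Day 1 predose list rather than from footnote g and 9.2.1. The Day 1 route is plausible: the dose is given at the end of a dialysis session that inclusion criterion 4.1.5 sets at 3 to 4.5 hours, so a symptom can be recorded in that session and worsen after the injection.

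AE incidence is the first-listed secondary endpoint and bears directly on the safety and tolerability hypothesis. For affected records the error is an under-count of on-treatment deterioration.

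**Working it through.** **1. The plan's own AE figure.** The only AE-related calculation is the chance of seeing at least one event among 24 subjects on AMG 416, which is 1 − (1 − p)^24.
- p = 0.01: 1 − 0.99^24 = 0.2143. The plan says 21%.
- p = 0.15: 1 − 0.85^24 = 0.9798. The plan says 98%.

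Both are reproduced and are not in dispute.

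**2. Tracing one condition through the rules.** It begins after consent and before first dose, and worsens after dosing.
- *Non-serious, site follows footnote g and 9.2.1.* There is no pre-dose AE record. The worsening is a new AE under 9.1.1 (or footnote c) with a post-dose start. **It is a TEAE.**
- *Held as medical history or as a hemodialysis symptom from screening.* Same result. **It is a TEAE.**
- *Non-serious, recorded before dosing under the synopsis wording or the Day 1 predose list.* The single-record rule keeps the pre-dose start and raises the grade. The flag marks it as pre-dose. **It is not a TEAE.**
- *Serious before first dose.* It is on record from consent whichever passage the site follows. **Its worsening is not a TEAE unless entered as a new event.** Section 9.2.2 does not say which to do.

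**3. Size per subject.** With about 24 subjects on AMG 416 and 8 on placebo, one misclassified subject moves the incidence of that event by 1/24 = 4.2 points or 1/8 = 12.5 points.

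**4. How many subjects.** The documents do not say, so these are assumptions only. Suppose 10% to 50% of subjects start an event in screening, one third of those events are ongoing at first dose, and one quarter of those worsen:
- 0.10 × 1/3 × 1/4 = 0.8%, and × 24 = 0.2 subjects
- 0.50 × 1/3 × 1/4 = 4.2%, and × 24 = 1.0 subject

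This treats every site as recording non-serious events before dosing, so under these inputs it is close to an upper bound. If only 10% to 50% of sites did so (also an assumption), the range is 0.2 × 0.10 = 0.02 to 1.0 × 0.50 = 0.5 subjects.

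**5. Effect on the detection figures.** Let f be the assumed share of affected subjects whose event sits on a pre-dose record, and replace p by p(1 − f):

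| f | p = 0.15 | p = 0.01 |
|---|---|---|
| 0 | 0.9798 | 0.2143 |
| 5% | 0.9750 | 0.2047 |
| 10% | 0.9692 | 0.1951 |
| 20% | 0.9535 | 0.1753 |
| 50% | 0.8460 | 0.1133 |

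The effect on detection is slight unless f is large, and nothing in the documents suggests that it is.

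**The case against.** The best defence is that the protocol's operational text is consistent. The synopsis sentence names no start and sends the reader to Section 7 and Table 1 for timing. Section 7.3.17 uses the same duration phrase but ties it to Sections 9.1 and 9.2. The Table 1a marks at screening and Day -2 carry footnote g, so they read as SAE monitoring, as the visit lists confirm. Section 7.3.5 sends abnormal examination findings at screening or Day 1 to medical history. A site following all this records no non-serious AE before dosing, and later worsening is counted.

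Much of that stands, and it rules out several stronger readings that a reader might infer:
- *That the protocol sets two flatly opposed start points.* It does not. Only the loose synopsis sentence and the Day 1 predose entry pull away from first dose.
- *That all worsening of conditions begun before dosing is lost.* Section 9.1.1 and footnote c capture worsening of history and hemodialysis symptoms.
- *That SAE worsening is lost at every site.* The single-record rule sits in the non-serious section and 9.2.2 does not repeat it. Nor does SAP 9.6.1 expressly limit the SAE table to treatment-emergent events.
- *That the SAP flag shows non-serious pre-dose AEs are expected, or that 8.3 excludes every pre-dose event.* The flag is needed for SAEs in any case, and the 8.3 sentence covers only partially missing start dates.

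A subject with another qualifying report of the same event is also still counted, since SAP 5.4 counts subjects once per event.

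What the defence does not answer is the record that does exist before dosing. For that record the SAP definition is a stated rule giving the wrong count, and no other passage corrects it.

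**Conclusion.** The point holds in a limited form. An event on an AE record before first dose that worsens on treatment is omitted from the TEAE tables unless the site enters the worsening separately. The protocol does not instruct sites to do so, and for non-serious events the single-record rule points the other way. Exposure is confined to pre-dose SAEs and to non-serious AEs recorded early on a looser reading of the synopsis or the Day 1 list.

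The number affected is probably small. The assumed ranges above stay at or below one subject in 24, but they rest on inputs that the documents do not supply. The consequence per subject, 4.2 or 12.5 points, follows directly from the group sizes. AE incidence here is secondary and descriptive, so no test, sample size or PK result changes. The correction is still worth making before database lock. If a record carries no date of worsening, the analyst cannot tell whether its worst grade fell before or after first dose.

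**What to change.** 1. **SAP 5.4.** Extend the TEAE definition to include an event present before first dose that increases in CTCAE grade or becomes serious on or after first dose, within the existing end of the window.
2. **Protocol 9.2.1 and 9.2.2, and the CRF completion note.** Make one exception to single-record handling: post-dose worsening of an event recorded before first dose is entered as a new event, with the date of worsening as onset. The SAP clause cannot be applied reliably without this date. Once the new record exists the clause is partly redundant, but it makes the intended count explicit.
3. **Synopsis and Day 1 predose list (7.2.3).** Align both with footnote g and 9.2.1: non-serious AEs from first dose, SAEs from consent.

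The cost is wording in two documents and a CRF note, plus one additional CRF entry for each of the few affected events. Reported TEAE incidence may come out slightly higher.
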